7.1.3 Chronicity of adverse events

The chronicity of the AE will be classified by the investigator on a three-item scale as defined below:

- Single occasion: single event with limited duration;
- Intermittent: several episodes of an event, each of limited duration;
- Persistent: event which remained indefinitely.

7.1.4 Action

Eventual actions taken will be recorded.

7.1.5 Serious adverse events

A Serious Adverse Event (SAE) is defined by the International Conference on Harmonization (ICH) guidelines as any AE fulfilling at least one of the following criteria:

- results in death;
- is life threatening (at the time of the event);
- requires hospitalisation or prolongation of existing inpatients' hospitalisation;
- results in persistent or significant disability or incapacity;
- is a congenital anomaly or birth defect; or
- any other important medical event that did not result in any of the outcomes listed above due to medical or surgical intervention but could have been based upon appropriate judgement by the investigator.

An elective hospital admission will not be considered as a SAE.

7.1.6 Suspected unexpected serious adverse reactions

A SUSAR (Suspected Unexpected Serious Adverse Reaction) is a SAE that is unexpected, (nature or severity of which is not consistent with the applicable product information (e.g., investigator's brochure for an unauthorised investigational product or summary of product characteristics for an

authorised product)) and suspected (a reasonable possibility of causal relationship with the CO2 challenge).

7.1.7 Reporting of serious adverse events

SAEs and SUSAR's will be reported according to the following procedure.

The investigator will report expedited the following SUSARs through the web portal ToetsingOnline to the EC:

SUSARs that have arisen in the clinical trial that was assessed by the EC;

The expedited reporting of SUSARs through the web portal ToetsingOnline is sufficient as notification to the EC, CA and the Dutch Medicines Evaluation Board, a separate notification is not necessary. To prevent a double notification, it must be indicated in ToetsingOnline if the SUSAR is reported in the EMA EudraVigilance database, this will prevent the notification of the CA and the Dutch Medicines Evaluation Board through the web portal ToetsingOnline.

The expedited reporting will occur not later than 15 days after the first knowledge of the adverse reactions. For fatal or life-threatening cases, the term will be maximal 7 days for a preliminary report with another 8 days for completion of the report.

7.1.8 Follow-up of adverse events

All AEs will be followed until they have abated, returned to baseline status or until a stable situation has been reached. Depending on the event, follow up may require additional tests or medical procedures as indicated, and/or referral to the general physician or a medical specialist.

7.2 Concomitant medications

Concomitant medications initiated, stopped, up-titrated or down-titrated for an AE will be recorded.

7.3 Temporary halt for reasons of subject safety

In accordance to section 10, subsection 4, of the WMO, the investigator will inform the subjects and the EC if anything occurs, on the basis of which it appears that the disadvantages of participation may be significantly greater than was foreseen in the research proposal. The study will be suspended pending further review by the EC, except insofar as suspension would jeopardise the subjects' health. The investigator will ensure that all subjects are kept informed.

7.4 Annual safety report or development safety update report

In addition to the expedited reporting of SUSARs, the investigator will submit, once a year throughout the clinical trial, a safety report to the EC, CA and CAs of the concerned Member States. This safety report consists of:

- a list of all suspected (unexpected or expected) serious adverse reactions, along with an aggregated summary table of all reported serious adverse reactions, ordered by organ system, per study;
- a report concerning the safety of the subjects, consisting of a complete safety analysis and an evaluation of the balance between the efficacy and the harmfulness of the medicine under investigation.

Submission of an annual safety update report is not deemed applicable to this study. Besides the inhalation of CO₂ as challenge model, no pharmacological compounds will be administered.

7.5 Pregnancy

If a woman becomes pregnant during the study, the investigator must counsel the subject and discuss the risks of continuing with the pregnancy and the possible effects on the foetus. Monitoring of the subject should continue until the outcome of the pregnancy is known. The subject must discontinue with the study when the subject is pregnant.

8 STATISTICAL METHODOLOGY AND ANALYSES

8.1 Statistical analysis plan

All safety and statistical programming are conducted with SAS 9.4 for Windows or newer (SAS Institute Inc., Cary, NC, USA).

8.2 Protocol violations/deviations

Protocol deviations will be identified based on conditions related to the categories below:

- Protocol entry criteria
- Forbidden concomitant medications
- Missing evaluations for relevant endpoints
- Other protocol deviations occurring during study conduct.

Major protocol deviations will be identified before the study closure and listed where appropriate.

8.3 Power calculation

Not applicable.

8.4 Missing, unused and spurious data

All missing or incomplete safety and PD data, including dates and times, are treated as such. Missing test results or assessments will not be imputed. Missing PD data, indicated as 'M' in the data listing, will be estimated within the statistical mixed model using SAS PROC MIXED.

The handling of missing, unused, and spurious data will be documented in the study report.

8.5 Analysis sets

Data of all subjects participating in the study will be included in the analyses if the data can meaningfully contribute to the objectives of the study.

8.5.1 Safety set

The safety population will be defined as all subjects who were validated (randomised) and received at least 1 dose of study treatment.

8.5.2 Pharmacodynamic analysis set

The analysis population for pharmacodynamics is defined as all subjects who were validated (randomised), performed at least one CO2 challenge, and have at least one post-baseline assessment of the parameter been analysed.

8.6 Subject disposition

Subject disposition will be listed by subject.

The following subject data will be summarized:

- number and percentage of subjects screened,
- number and percentage of subjects enrolled,
- number and percentage of subjects completed,
- number and percentage of subjects included in safety population and
- number and percentage of subjects included in the PD analysis population.

A subject who completed the study is defined as a subject which performed 5 CO₂ challenges adequately.

8.7 Baseline parameters and concomitant medications

8.7.1 Demographics and baseline variables

Continuous demographic variables (e.g., age, height, weight, BMI) will be summarized by descriptive statistics (n, mean, SD, median, Min, Max).

Qualitative demographic characteristics (sex, race/ethnicity) will be summarized by counts and percentages.

8.7.2 Medical history

Medical history will only be listed.

8.7.3 Concomitant Medications

Previous and concomitant medications will be listed by International Nonproprietary Names, dose, regimen, route and for which indication it was prescribed.

8.8 Safety and tolerability endpoints

The safety set is used to perform all safety analyses.

Baseline is defined as the average value prior to conducting the CO2 inhalation challenge. Change from baseline will be calculated for all continuous safety parameters.

8.8.1 Adverse events

The AE coding dictionary for this study will be Medical Dictionary for Regulatory Activities (MedDRA). It will be used to summarize AEs by primary system organ class (SOC) and preferred term (PT).

All adverse events will be displayed in listings.

A treatment-emergent adverse event (TEAE) is defined as an adverse event observed after starting the CO2 challenge. If a subject experiences an event both prior to and after starting administration of the CO2 challenge, the event will be considered a TEAE only if it has worsened in severity (i.e., it is reported with a new start date) after starting administration of the specific treatment, and prior to the start of another treatment, if any. All TEAEs collected during the investigational period will be summarized.

The number of and the number of subjects with treatment emergent AEs will be summarized by:

- 1. treatment, MedDRA SOC and PT;
- 2. treatment, MedDRA SOC, PT and severity;
- 3. treatment, MedDRA SOC, PT and drug relatedness.

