1.2.2 Study population

A total of 20 healthy subjects, who previously have shown to be sensitive to the panicogenic effects of the CO2 challenge, of either gender will be enrolled into the study following satisfactory completion of a screening (ECG and medical history) where eligibility for the study will be checked.

1.2.3 Comparative drug(s) and/or placebo Not applicable.

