1.2.4 Treatment duration

The total study duration will be 29 (+/-3) days, and subjects will undergo the CO2 inhalation challenge in total five times on Day 1, Day 8 (+/-3), Day 15 (+/-3), Day 22 (+/-3) and Day 29 (+/-3) of the study. No treatment will be administered.

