3 STUDY DESIGN

3.1 Overall study design and plan

Five visit trial to investigate the dose-response relationship, test-retest reliability, and tolerance to repeated exposure of the 35% carbon dioxide experimental panic challenge in 20 CO2-sensitive healthy volunteers.

[figure not shown]
Out of the five scheduled visits (Figure 1):

- single or a double vital capacity inhalation of 35% CO2/65% O2 will be randomized over a 2-way cross-over part consisting of visit 1 and visit 2. During the first visit, half of the participants (n=10) will be randomized to receive a single vital capacity inhalation of CO2 while the other half (n=10) will be randomized to double vital capacity inhalation of CO2. Approximately a week later, the groups will switch, with the group originally assigned the single vital capacity inhalation now receiving the double vital capacity inhalation, and vice versa.
- visits 3, 4 and 5 will follow a fixed pattern, with all participants receiving only double vital capacity 35% CO2/65% O2 inhalation roughly a week apart.

On the first day, prior to the CO2 challenge, the Spielberger State-Trait Anxiety Inventory (STAI), Dutch Personality Questionnaire (DPQ), and Cloninger Temperament Character Inventory (TCI) will be administered according to the schedule of assessments (Table 1).

To evaluate the severity of panic symptoms, each subject will complete the PSL-IV, VAS Fear and VAS Discomfort within five minutes before and as soon as possible (but no later than 15 minutes) after the CO2 challenge according to the schedule of assessments (Table 1). In addition, the STAI Y1 will be administered within 20 minutes before and as soon as possible after the CO2 challenge. Throughout the procedure, vital signs such as blood pressure and heart rate will be continuously monitored. Lastly, biomarkers for neuroendocrine autonomic nervous system activation (plasma ACTH, cortisol, and prolactin; saliva alpha-amylase and cortisol) and plasma orexin-1 will be assessed according to the schedule of assessments (Table 1).

Figure 2: Schematic overview of design.

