8.9 Pharmacodynamic endpoints

The final analysis will be preceded by a data review which consists of individual graphs per visit by time of all pharmacodynamic measurements by time. The graphs will be used to detect outliers and measurements unsuitable for analysis.

The PD parameters will be listed by treatment, subject, visit and time. Individual graphs by time will be generated.

All repeatedly measured PD endpoints will be summarized (n, mean, SD, SEM, median, Min and Max values) by treatment and time, and will also be presented graphically as mean over time, with standard deviation as error bars. The occurrence of PAs will be summarized in a frequency table.

Parameters will initially be analysed without transformation, but if the data suggest otherwise, log-transformation may be applied. Log-transformed parameters will be back-transformed after analysis where the results may be interpreted as percentage change.

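### Adverse event and PD summaries by treatment set one single challenge per subject against up to four pooled double challenges, so the descriptive columns are not comparable

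*Protocol*

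**What the plan says.** The design is unbalanced in exposure. Section 1.2.4 states that "subjects will undergo the CO2 inhalation challenge in total five times on Day 1" and at four roughly weekly visits after it. Under section 3.1, visits 1 and 2 are a randomised crossover giving each subject one single and one double inhalation; after that, "visits 3, 4 and 5 will follow a fixed pattern, with all participants receiving only double vital capacity" inhalation.

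Section 8.8.1 includes every treatment-emergent event of the investigational period. "The number of and the number of subjects with treatment emergent AEs will be summarized by" three groupings, the first being "treatment, MedDRA SOC and PT". The other two add severity and relatedness, again under treatment. None mentions visit, challenge number or number of challenges.

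For pharmacodynamics, section 8.9 says that repeatedly measured endpoints "will be summarized (n, mean, SD, SEM, median, Min and Max values) by treatment and time". The listings described just before that sentence are sorted by treatment, subject, visit and time, so visit is kept in the listings and dropped from the summaries.

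The word *treatment* is not defined. Section 1.2.4 says that none is given, and the table in 5.1.1 enters the number of treatments as not applicable.

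**The concern.** If the two columns are single and double, the double column accumulates four times the exposure of the single column. More events, and more subjects with an event, would then appear under double even if one double inhalation carried exactly the risk of one single inhalation. Section 1.2.1 gives a lower burden on subjects as one reason for the study, so a reader may well look at these tables to compare the two procedures.

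The PD summaries raise a different problem. A mean does not grow with the number of exposures. However, a double mean pooled over visits mixes early and late challenges, whereas single occurs only at visit 1 or 2. Whether the response changes with repetition is itself a primary objective.

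**Working it through.** The protocol gives no adverse event rate and no power calculation (8.3), so there is no figure of its own to reproduce.

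**Inputs**
- Subjects: 20 (1.2.2).
- Challenges per subject: 5 (1.2.4).
- Visits 1 and 2: one single and one double; visits 3 to 5: three doubles (3.1).
- Per-challenge event risk *p*: not given. Assumed equal for both types, 5% to 50%, with at most one event counted per challenge.
- Within-subject correlation ρ: not given. Range 0 to 1, beta-binomial model.

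**1. Exposure.** Single: 20 × 1 = 20 challenges. Double: 20 × (1 + 3) = 80.

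**2. Events.** Expected counts are 20*p* and 80*p*. The ratio is 4 whatever *p* and ρ are.

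**3. Subjects with at least one event, independent challenges.** Single: *p*. Double: 1 − (1 − *p*)^4.

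| *p* | Events, single v double | Subjects, single | Subjects, double |
|---|---|---|---|
| 5% | 1 v 4 | 5% | 18.5% |
| 10% | 2 v 8 | 10% | 34.4% |
| 20% | 4 v 16 | 20% | 59.0% |
| 30% | 6 v 24 | 30% | 76.0% |
| 50% | 10 v 40 | 50% | 93.8% |

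**4. Correlated challenges.** With a = *p*(1/ρ − 1) and b = (1 − *p*)(1/ρ − 1), the double share is 1 − b(b+1)(b+2)(b+3) / [(a+b)(a+b+1)(a+b+2)(a+b+3)]. At *p* = 20% and ρ = 0.5, a = 0.2 and b = 0.8, so the share is 1 − (0.8 × 1.8 × 2.8 × 3.8)/(1 × 2 × 3 × 4) = 1 − 0.638 = 36.2%. At ρ = 0.2 it is 48.4%, at ρ = 0.8 it is 26.1%, and it equals the single figure of 20% only at ρ = 1.

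**5. With a fair denominator.** Per challenge: 20*p*/20 = 80*p*/80 = *p*, ratio 1. On visits 1 and 2 only: 20 single v 20 double, ratio 1 for events and for subjects.

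**6. PD summaries.** With the two sequences equally frequent, the average visit position is 1.5 for single and (1.5 + 3 + 4 + 5)/4 = 3.375 for pooled double. Plasma and saliva biomarkers are taken only on Days 1, 8 and 29 (Table 1), so two doubles are pooled and the position is (1.5 + 5)/2 = 3.25. If the SEM is computed on all 80 double values as separate observations, then under an exchangeable correlation ρ the true standard error is larger by about √(1 + 3ρ): √2.5 = 1.58 times at ρ = 0.5.

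**The case against.** The strongest reply is that the protocol never says that the four doubles are pooled. If each challenge is its own treatment (single, double 1 to 4), the imbalance disappears, and column definitions are often settled in the analysis plan or table shells. It stands that the term is undefined and that single versus double is a reading. It is nevertheless the natural one. Section 8.9 names treatment and visit as separate sorting keys and then summarises without visit, and 8.8.1 refers to the start of another treatment. The protocol has thus stated a grouping rule, and under its natural reading that rule gives non-comparable columns.

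Three stronger readings might be inferred, and the documents do not support them:
- *That a planned tolerability comparison is biased.* Section 2 lists no objective or endpoint comparing adverse events between inhalation types. No adverse event test is planned, and all events are listed, so the exposure can be recovered.
- *That PD means are inflated in the same way as counts.* They are not; the problem is blending over visits. If the response fades with repetition, pooling lowers the double mean; if it grows, pooling raises it.
- *That the tolerance analysis is lost.* Sections 8.9.2 to 8.9.4 model challenge number, and 8.9 also provides individual graphs per visit.

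The independence figures are also the largest gap among the non-negative correlations considered, and should not be quoted alone.

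**Conclusion.** The point holds for the descriptive tables, provided that *treatment* means single versus double. At equal per-challenge risk the expected event ratio is then 1:4 by arithmetic if all challenges are completed. The excess in subjects with an event under double depends on two quantities that the protocol does not give. At an assumed 20% risk it ranges from 59% v 20% under independence, through about 36% v 20% at correlation 0.5, to no excess at perfect correlation.

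The PD summaries have a related but distinct weakness: a double mean that mixes in any tolerance or visit effect, and an SEM that is too small when values from the same subject are positively correlated. No inferential result by challenge number changes. The point deserves correction because the randomised crossover already provides a balanced comparison that these summaries do not use.

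**What to change.** - In sections 8.8.1 and 8.9, define *treatment*.
- Summarise adverse events and PD endpoints by inhalation type and challenge number (single; double 1, 2, 3, 4), and show the number of challenges in each column as the denominator.
- Base any descriptive single-versus-double statement, for adverse events or PD, on visits 1 and 2, where each subject has one of each.

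The cost is a few sentences and more table columns, with no change to conduct or data collection. The small downside is that the single-versus-double comparison then uses 20 double challenges instead of 80. The other 60 remain visible in their own columns.

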8.8.2 ECG

At each time point, absolute values and change from baseline of ECG numeric variables will be summarized with the number of samples (n), mean, SD, SEM, median, Min, and Max values. The number of available observations and out-of-range values (absolute and in percentage) will be presented. Values outside the investigator's normal range will be flagged in the listing. 'H' and 'L', denoting values above or below the investigator reference range (when present), will flag out-of-range results.

8.9 Pharmacodynamic endpoints

The final analysis will be preceded by a data review which consists of individual graphs per visit by time of all pharmacodynamic measurements by time. The graphs will be used to detect outliers and measurements unsuitable for analysis.

The PD parameters will be listed by treatment, subject, visit and time. Individual graphs by time will be generated.

All repeatedly measured PD endpoints will be summarized (n, mean, SD, SEM, median, Min and Max values) by treatment and time, and will also be presented graphically as mean over time, with standard deviation as error bars. The occurrence of PAs will be summarized in a frequency table.

Parameters will initially be analysed without transformation, but if the data suggest otherwise, log-transformation may be applied. Log-transformed parameters will be back-transformed after analysis where the results may be interpreted as percentage change.

8.9.1 Occurrence of PAs

The difference in response between single and double vital capacity 35% CO2/65% O2 in terms of the occurrence and intensity of PAs in CO2 sensitive healthy subjects, which is assessed with the Panic Symptoms List-IV (PSL-IV), VAS Discomfort, and VAS subjective fear.

For the occurrence of PAs repeated measures logistic regression will be used with challenge (single/double) as fixed factor and subject as random factor.

For the intensity of Pas repeated measures mixed model ANCOVA with challenge (single/double) as fixed factor, subject as random factor and baseline as covariate will be used.

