1.2.6 Statistical hypotheses and sample size

This is an observational, methodological study; therefore, the sample size is not based on statistical considerations. We've chosen a sample size of 20 participants because our current database includes 180 individuals sensitive to the panic-inducing effects of the CO2 challenge. Based on our previous experiences, selecting 20 participants from this group for the study is realistic.

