4.2 Inclusion criteria

- 1. Healthy male or female aged between 18 and 65 years (inclusive) at screening who have been demonstrated to be sensitive to the panicogenic effects of the CO2 challenge in previous studies.
- 2. Sensitivity to the fear-inducing effects of 35% CO2 double-breath inhalation is defined as an increase from pre-CO2 to post-CO2 challenge in the following: PSL-IV total scores ≥4 with at least 1-point increase for at least 4 of the symptoms specified in the PSL-IV and an increase on the Visual Analog Scale (VAS) Fear of at least 25 mm.
- 3. BMI of 18-32 kg/m₂ (inclusive).
- 4. Non-smoker for at least 3 months.

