8.9.3 Occurrence of tolerance after repeated exposure

The occurrence and intensity of PAs in CO2 sensitive healthy subjects caused by a double (and single) vital capacity inhalation of 35% CO2/65% O2.

For the occurrence of PAs repeated measures logistic regression will be used with challenge number as fixed factor and subject as random factor.

The intensity of PAs will be analyzed with repeated measures mixed model ANCOVA with challenge number as fixed factor, subject as random factor and baseline as covariate.

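### The only inferential analysis of panic-attack occurrence, a random-subject logistic regression in 20 pre-selected responders, has no finite odds ratio whenever nobody panics on the single breath only

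*Protocol*

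**What the plan says.** Section 1.1 hypothesises that a higher percentage of subjects panic after the double than after the single inhalation.

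For this comparison Section 8.9.1 states: "For the occurrence of PAs repeated measures logistic regression will be used with challenge (single/double) as fixed factor and subject as random factor". For tolerance Section 8.9.3 states: "For the occurrence of PAs repeated measures logistic regression will be used with challenge number as fixed factor and subject as random factor". Section 8.9.4 and the synopsis name the same model. None of these places names an estimation method, a test statistic, or an exact, conditional or penalised alternative.

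The only other output on occurrence is descriptive (Section 8.9): "The occurrence of PAs will be summarized in a frequency table". Intensity is analysed separately by mixed-model ANCOVA.

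Under Section 4.2, subjects are people "who have been demonstrated to be sensitive to the panicogenic effects of the CO2 challenge in previous studies". The threshold is set on the double breath: "Sensitivity to the fear-inducing effects of 35% CO2 double-breath inhalation is defined as an increase from pre-CO2 to post-CO2 challenge", with "PSL-IV total scores ≥4 with at least 1-point increase for at least 4 of the symptoms specified in the PSL-IV" and a VAS Fear rise of at least 25 mm. On numbers, Section 1.2.6 says that "the sample size is not based on statistical considerations" and that "selecting 20 participants from this group for the study is realistic". Section 8.3 gives no power calculation.

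**The concern.** Selecting on the double-breath response makes a high panic rate on double foreseeable. With 20 subjects, very few or none may then panic on the single breath but not on the double. Those few subjects are what keep the odds ratio of a random-subject logistic model finite. Without them the model returns no usable estimate or Wald interval for the protocol's own hypothesis, and this happens when the paired data all point in the hypothesised direction.

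The study is not blinded (Section 5.1.2). A substitute test chosen after the model had failed would therefore be data-driven, and Section 8.10 denies such inference confirmatory value.

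**Working it through.** The plan states no panic rate, alpha or power, so it has no figure to reproduce. The inputs are N = 20 with each subject having both inhalations (Section 3.1), the model of Section 8.9.1, and assumed panic rates.

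**1. When the estimate is infinite.** Classify subjects as both / double only / single only / neither. Let b be the log odds ratio of double against single. In a random-intercept logistic model every subject satisfies P(double only) / P(single only) = exp(b), whatever the intercept. If single only is 0 and double only is above 0, the likelihood keeps rising as b grows (with the subject SD growing too if some panic on neither). It approaches the saturated likelihood and never reaches it. Minus log-likelihood, maximised over the other parameters:

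| Counts | b=0 | 2 | 4 | 8 | 12 | Saturated limit |
|---|---|---|---|---|---|---|
| 12 / 8 / 0 / 0 (double 20/20) | 20.02 | 14.96 | 13.70 | 13.465 | 13.460 | −(12 ln 0.6 + 8 ln 0.4) = 13.460 |
| 10 / 6 / 0 / 4 (double 16/20) | 24.75 | 21.36 | 20.70 | 20.595 | 20.593 | −(10 ln 0.5 + 6 ln 0.3 + 4 ln 0.2) = 20.593 |

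So 20/20 on double is sufficient (given fewer on single) but not necessary. One single-only subject restores a finite fit: 11 / 8 / 1 / 0 gives b = 2.5, SE 1.1, Wald p = 0.024.

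**2. What each test reports when double is 20/20.** With d subjects panicking on double only, exact McNemar p = 2 × 0.5^d. The likelihood-ratio (LR) statistic is twice the drop in minus log-likelihood; for 12/20 it is 2 × (20.016 − 13.460) = 13.1 on 1 df.

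| Single | d | Exact p | LR p |
|---|---|---|---|
| 16/20 | 4 | 0.125 | 0.014 |
| 15/20 | 5 | 0.0625 | 0.0057 |
| 14/20 | 6 | 0.031 | 0.0022 |
| 12/20 | 8 | 0.0078 | 0.0003 |
| 10/20 | 10 | 0.0020 | 0.00003 |

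For 12/20 against 20/20 the random-intercept fit stopped at b of about 20 with SE about 5,200, so Wald p = 0.997. The exact value depends on where the optimiser stops. An ordinary logistic fit to the same counts gives 0.98 after 15 iterations and 1.0 after 25.

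**3. How often this occurs.** Let q be P(single only) and r be P(double only). The chance of no single-only and at least one double-only subject is (1 − q)^20 − (1 − q − r)^20. The second term is negligible here. The rates are assumptions. The latent model has a normal subject effect and unit residual SD.

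| Double/single | Independent visits | Subject SD 0.7 | Subject SD 1.2 |
|---|---|---|---|
| 70%/50% | q=0.150: 4% | q=0.104: 11% | q=0.064: 26% |
| 80%/50% | q=0.100: 12% | q=0.063: 27% | q=0.033: 51% |
| 90%/60% | q=0.060: 29% | q=0.037: 47% | q=0.018: 70% |

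For example, at 80%/50% and SD 0.7, 0.937^20 = 0.27. The independent-visits column is a floor, because repeated responses in one subject will be positively correlated.

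**4. Tolerance model (Section 8.9.3).** A challenge at which all 20 panic has no finite coefficient, and neither do its contrasts with other challenges. The chance at one double challenge is p^20: 1.2% at p = 0.80, 12.2% at 0.90 and 35.8% at 0.95. For at least one of the four double challenges it is about 4-5%, 34-38% and 73-79%, allowing for within-subject correlation.

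**The case against.** The strongest reply is that the protocol fixes a model class and not a Wald test. A reader might infer that the plan would miss the clearest possible effect. The documents do not support that: no test statistic is named, and an LR test of the same model gives p = 0.0003 for 12/20 against 20/20. In the tolerance model an omnibus LR test of challenge number also remains available. This stands, but only in part. The LR test supplies no finite odds ratio or upper confidence limit. With 20 pairs its p-values are also far below the exact ones (0.014 against 0.125 at 16/20), so it may be too liberal to rely on alone.

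A reader might also infer that occurrence has no other analysis. It has a frequency table, and intensity has its own ANCOVA for the same objectives. What is missing is a second inferential analysis of occurrence.

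The panic rates may also lie below the ceiling. Section 1.2.1 raises possible tolerance, Section 1.1 says lasting sensitivity is unclear, and selection on an earlier threshold invites regression to the mean. That makes 20/20 uncommon at 80% or below. It does not remove the problem in Section 8.9.1, which does not need 20/20. If nobody's response differs between the two inhalations, there is no effect to miss.

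Finally, a rule for non-convergence commonly sits in the SAP, and one not shown here may contain it. The point is not that such a rule is absent. The model that the protocol does name suits foreseeable data poorly.

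**Conclusion.** The point holds as a weakness of the chosen analysis that should be corrected; it does not show that the study cannot detect an effect. For single versus double, the planned odds ratio has no finite estimate whenever some subjects panic on double only and none on single only. Under the assumed rates this affects about 11-26% of trials at 70%/50%, 27-51% at 80%/50% and 47-70% at 90%/60%. These figures rest on rates that the documents do not give and on a latent subject SD of 0.7 to 1.2 against a unit residual; weaker within-subject correlation lowers them towards 4%, 12% and 29%. In those trials a Wald test or interval is uninformative, and an LR test gives a p-value without a usable effect size. The tolerance model has the same difficulty for any challenge at which every subject panics.

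**What to change.** In Section 8.9.1, make the main occurrence analysis an exact McNemar test on the visit 1-2 pairs, or its period-adjusted exact form (Mainland-Gart). Report the paired risk difference with a score-based 95% CI; this estimates the hypothesised difference in percentages directly and stays defined under separation. Keep the random-subject logistic model as supportive.

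In Section 8.9.3, pre-specify a method that is not broken by separation: Firth-penalised logistic regression, or a permutation Cochran Q test where a test alone is enough. Apply it regardless of the observed counts, so that the choice is not triggered by the data.

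The cost is wording only, and Section 9.5.1 classes other statistical analyses as a non-substantial amendment. There are two statistical costs. Exact tests are somewhat conservative: with no single-only subject, six double-only subjects are needed for two-sided p below 0.05 (2 × 0.5^6 = 0.031; five give 0.0625). McNemar also drops incomplete pairs, which the supportive logistic model can still use.
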